Adolescent Health Club Component and Evaluation: Households with AGYW ages 15 to 25 will be identified by community health workers from randomly selected block sectors of the study area. Clubs will be conducted in separate neighborhood sectors, to limit contamination. Conducting club meetings near to the lanes adolescent girls live in will make it easier for them to attend. To further assess and address potential contamination, we will ask individuals to verify the adolescent health club they attended in the post-intervention survey, whether they attended an additional health club outside our intervention (such as, in school). If any contamination is evident based on this question, then we will model it. AGYW and their mothers (if unmarried and under the age of 18) will be approached by a member of the research team and the adolescent health club intervention will be explained. If consent is obtained, the AGYW will be enrolled, and randomized to either participate or join the wait-list. AGYW will complete the pre-intervention evaluation instrument upon enrollment. In addition to the activities in the "It's All One" Curriculum spread over eight modules, providers from the sensitization component will attend one meeting to discuss services available in the adolescent-friendly clinics, and hear young women's previous experiences accessing care. Similar to the process for the provider sensitization component, the facilitator will complete a log after each session to code activities as implemented fully, implemented partially or modified significantly and describe any changes. The log will also include a section to document any unusual events associated with any of the sessions, and the effect of these events on implementation, acceptability, or feasibility. Every other session will be observed and documented in fieldnotes that will be analyzed to contribute to process evaluation (see analysis details below). As with the provider component, the log and fieldnotes will enable a qualitative assessment of intervention fidelity. When young women complete the curriculum, they will also complete the post-intervention evaluation instrument. A sub-sample of young women (N=15) will be asked to participate in a focus group discussion to reflect on the club's impact and acceptability. Domains measured by previously validated instruments^(32, 48, 66, 123-126) to be covered in the pre- and post-intervention surveys are shown in Table 3. There are relatively few validated quantitative measures of implementation outcomes,^(127, 128) and none in Hindi, thus the measure we have chosen⁽¹²⁹⁾ will have to be translated and back-translated to ensure comprehension.

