
Table 1: Domains to be covered in AGYW pre- and post-intervention surveys.

Pre-Intervention Survey Domains	Post-Intervention Survey Domains

Demographics	Demographics
Clinic service uptake/use	Clinic service uptake/use ^(32, 130)
SRHR knowledge	SRHR knowledge ^(123, 131)
Violence and safety	Violence and safety ^(124, 125)
Gender norms	Gender norms ^(48, 132)
Agency	Agency ^(66, 133)
Mental health	Mental health ⁽¹²⁶⁾
	Intervention acceptability ⁽¹²⁹⁾
	Satisfaction with intervention/services ⁽¹²⁸⁾
	Feasibility ⁽¹²⁸⁾

Intervention Power Calculation and Sample Size Considerations: Power calculations and sample size for the adolescent health club component are determined based on the SRH knowledge measure.⁽¹²³⁾ With 85% power, in a two-arm comparison design (similar to round one in Figure 2 above), and based on data from a previous intervention study⁽¹³¹⁾ in which the investigators found a pre/post intervention difference of 1.3 and a standard deviation of 3, we will need 50 pairs or 100 participants in the adolescent clubs total. Broken into four groups, I plan for each group to be 25 participants. As this calculation does not take into consideration within-group analysis, it is a ≈20% overestimate, which allows for 20% loss to follow-up, or participant drop-out without loss of statistical power. However, to minimize bias, I am targeting 95% follow-up. 95% follow-up is based on our team's procedures for tracking and retaining adolescent health club participants. Specifically, we will make clear the participation expectations upon recruitment, consent, and the initial health club meeting. We will follow-up with participants who miss club sessions via cell phone and home visits as needed. These methods have been used by the research team in previous studies in the study area.

Implementation and Intervention Data Analysis

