For the provider/staff sensitization component, a total of N=60 providers and staff will be recruited from the public and private clinics where AGYW were recruited for the formative quantitative survey. There will be two separate groups of 20 people each who undergo the sensitization workshop. The workshop will take place over four days. In previous work in the study area, retaining providers for a short intervention such as the one described in this proposal has not been a challenge and therefore we anticipate no challenges in recruiting the required sample size.

For the adolescent health club component, households with AGYW between the ages of 15 and 25 will be identified by Apnalaya's field team from randomly selected block sectors of the study area. AGYW and their mothers (if unmarried and under the age of 18) will be approached by a member of the research team and the adolescent health club intervention will be explained. If consent is obtained, the AGYW will be enrolled to either participate in the health club immediately or join the wait-list. An initial sample of 50 AGYW will be recruited (one group of 25 to begin intervention immediately, and one wait-list group). After the first intervention group has completed the health club curriculum, the wait-listed group will begin the intervention, and another 25 AGYW will be recruited for a wait-list. This will continue until four groups of 20-25 AGYW complete the health club intervention. Factoring in an attrition rate of 20%, the expected N at endpoint is 80. AGYW will complete the pre-intervention evaluation instrument upon enrollment. When young women complete the health club curriculum, they will also complete the post-intervention evaluation instrument. A sub-sample of young women will be asked

to participate in a focus group discussion to reflect on the club's impact and acceptability. To limit differences in

the time needed to assemble the health club groups, we will avoid recruiting during busy religious festivals/holidays (such as Ramadan) or vacation periods.

b. Describe how potential subjects are contacted.

Key informants and healthcare providers/staff for all phases will be contacted in the following ways: through in-person meetings, and snowball referrals/introductions via email (email recruitment template is attached) or cell phone.

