Identifiable data (email addresses and/or cell phone numbers) will be destroyed by [name] after the participant has completed study activities or when requested by the participant (whichever occurs first).

6. If appropriate, has a Certificate of Confidentiality been obtained?
 Yes, as this application is pending NIH funding.

SECTION V: POTENTIAL BENEFITS

Potential Benefits: Identify any benefits that may be reasonably expected to result from the research, either to the subject(s) or to society at large. (Payment of subjects is not considered a benefit in this context of the risk benefit assessment.)

The benefits to providers/health staff is developing better skills and techniques for working with AGYW and implementing better patient care practices. The benefits to AGYW are learning about their health and rights, coping skills, developing empowerment/agency with respect to SRH, and external resources over the course of the health club intervention. They also have the opportunity to contribute to improvements in community healthcare and other resources for AGYW in the community.

SECTION VI: RESEARCH ALTERNATIVES AND ECONOMIC CONSIDERATIONS

1. **Alternatives:** What other alternatives are available to the study subjects outside of the research?

Participants are free to decline to participate, or may end their participation at any point in time. Adolescent girls and young women may decline to participate, and it will not affect their access to services or standard of care in the community.

2. **Payments for Participation (Economic Considerations):** Describe any payments that will be made to subjects, the amount and schedule of payments, and the conditions for receiving this compensation.

AGYW will receive a small payment for their participation. For qualitative interviews and the quantitative survey in the formative phase, participants will receive 200 Indian rupees (approximately equivalent to \$2.80USD) for their time spent in the interview (estimated to last 30 minutes to an hour). These payments will be provided at the conclusion of the interview/survey. For participation in the intervention session, participants will receive 200 rupees for each session they attend, to be paid at the end of each session.

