Key informants who are in management positions, are healthcare providers, and/or work for the government will not receive a payment. Frontline key informants (community health workers, NGO field staff, daycare/childcare workers) and parents will receive the same payment as AGYW (200 INR or approximately \$2.80 USD) for their time in the key informant interviews. Lunch/snack will be provided to the healthcare providers and staff who attend the facility-based intervention, as well as KIIs who attend the theatre testing group sessions.

For physicians who participate in the facility-based intervention, they will receive 5,000 INR (approx. \$60 USD) upon completion of the intervention, or a portion of that depending on how many sessions they attend. CHVs will receive 1000 INR (approx. \$12 USD) upon completion of their intervention sessions, or a portion of that depending on how many sessions they attend. These amounts are to compensate them for their time, defray transportation expenses, and are based on recommendations of Indian colleagues who have conducted similar interventions with health providers in the past.

3. **Costs for Participation (Economic Considerations):** Clearly describe the subject's costs associated with participation in the research, and the interventions or procedures of the study that will be provided at no cost to subjects.

The only potential costs associated with participation are participants' time, and possibly the cost of transportation to reach the intervention sessions. Efforts will be made to conduct intervention sessions at centrally located venues, and/or venues the participants already go to (such as the Urban Health Center). In addition, adolescent girls and young women will receive a small payment for their time (between 2-16 USD depending on the time and extent of participation), which will help defray the costs of transportation.

4. **In Case of Injury:** This section is required for any research involving more than minimal risk, and for minimal risk research that presents the potential for physical harm (e.g., research involving blood draws).

N/A

- a. Will medical treatment be available if research-related injury occurs? *Write here*
- b. Where and from whom may treatment be obtained? *Write here*
- c. Are there any limits to the treatment being provided? *Write here*
- d. Who will pay for this treatment? *Write here*
- e. How will the medical treatment be accessed by subjects? *Write here*

IMPORTANT REMINDERS

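### No payment is stated for the health club post-survey, and payment, tracing and survey timing all follow attendance, so losses may fall on low attenders and inflate the pre/post gain

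*Combined protocol and SAP*

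**What the plan says.** - **Payments (Section VI, item 2).** The item opens with a general statement: "AGYW will receive a small payment for their participation". It then lists two kinds of payment for adolescent girls and young women. For the formative phase: "For qualitative interviews and the quantitative survey in the formative phase, participants will receive 200 Indian rupees". For the clubs: "participants will receive 200 rupees for each session they attend, to be paid at the end of each session". The club pre- and post-surveys are not mentioned.
- **Total (Section VI, item 3).** The total per young woman is put at "between 2-16 USD depending on the time and extent of participation".
- **Sessions and surveys (Section I, item 4, Adolescent Health Club Component and Evaluation).** The curriculum is "spread over eight modules"; the number of sessions is not given. At the start, "AGYW will complete the pre-intervention evaluation instrument upon enrollment". The post-survey comes when a woman completes the curriculum. Section III, item 3a says the same. Neither gives a time point for a woman who stops attending.
- **Tracing.** The power and sample size paragraph of Section I, item 4 describes phone calls and home visits for women who miss club sessions. Section IV, item 1 lists what phone numbers are for in the intervention phase: recruitment, session scheduling and missed sessions. Survey follow-up is not on the list.
- **Follow-up.** The power and sample size paragraph says "However, to minimize bias, I am targeting 95% follow-up". Section III, item 3a says "Factoring in an attrition rate of 20%, the expected N at endpoint is 80".
- **Analysis (Section I, item 4, Quantitative analysis).** Paired t-tests are preliminary and repeated-measures mixed models are primary. No method for missing outcomes is given, and attendance is not mentioned.

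**The concern.** The post-survey supplies the second half of every pre/post comparison, including SRH knowledge, the outcome on which the study is sized. Three things could bring a woman to it: money, tracing and a scheduled date. As written, each depends on her coming to sessions. A woman who drifts away has no stated payment to return for, is traced for missed sessions rather than for the survey, and has no survey date because she never completes the curriculum.

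If such women also learn less, which is plausible for a session-based curriculum, the women analysed over-represent regular attenders and the mean gain is too high. The issue is bias rather than precision.

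**Working it through.** **1. Does the payment range leave room for survey payments?**
Inputs: 200 INR per session; 2-16 USD in total; eight modules. The plan uses two exchange rates, both in Section VI, item 2: 200 INR is about 2.80 USD, and 5,000 INR is about 60 USD, so 200 INR is 60 × 200/5,000 = 2.40 USD. Assumption: one session per module.
- Reproducing the stated range: at a rounded 2 USD per session, 1 to 8 sessions give 2 to 16 USD. The range fits session payments alone.
- At the plan's own rates: 8 × 200 = 1,600 INR, which is 8 × 2.40 = 19.20 USD or 8 × 2.80 = 22.40 USD. Both exceed 16 USD.

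So on this assumption neither calculation leaves room for a survey payment. This supports the reading that the surveys are unpaid but does not prove it.

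**2. Planned retention.**
100 × (1 − 0.20) = 80, as Section III, item 3a states. The Section I target of 95% gives 95 women.

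**3. Size of the bias if loss falls on low attenders.**
Let *f* be the fraction followed up, *g* = 1.3 the mean gain in the women observed (the plan's figure), and *r* the gain in missing women as a fraction of *g*. The documents give no value for *r*; 0 to 0.5 is an assumption.

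Full-sample gain = *f* × *g* + (1 − *f*) × *r* × *g*; overstatement = *g* / full-sample gain − 1.

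| Follow-up | *r* | Full-sample gain | Overstatement |
|---|---|---|---|
| 95% | 0 | 0.95 × 1.3 = 1.235 | 5.3% |
| 95% | 0.5 | 1.235 + 0.05 × 0.65 = 1.2675 | 2.6% |
| 80% | 0 | 0.80 × 1.3 = 1.04 | 25% |
| 80% | 0.5 | 1.04 + 0.20 × 0.65 = 1.17 | 11% |

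At *r* = 1 there is no bias at any follow-up.

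**4. Precision is not the problem.**
Take the plan's difference of 1.3 and SD of 3 as a paired comparison at two-sided 5% (the plan states no alpha). The noncentral *t* gives 85.2% power with 50 pairs, which reproduces the plan's 85%. With 80 pairs it gives 97%.

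**5. Cost of paying for the post-survey.**
100 × 200 = 20,000 INR, or 100 × 2.40 = 240 USD to 100 × 2.80 = 280 USD.

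**The case against.** - **Silence is not exclusion.** The general sentence in Section VI, item 2 could cover the surveys, and they may in fact be paid. This stands. The point is that no payment is stated and that the range fits session-only payment. If the surveys are paid, the item is incomplete and still needs the sentence.
- **The surveys are not singled out.** A reader might infer that the outcome surveys are the only unpaid contacts. The documents do not support that: no cash payment is stated for young women in the focus group or the theater testing either. The list may simply be incomplete.
- **The survey could be held at the last paid session.** Its day and place are not given. That would help with women still attending, but not with those who have stopped.
- **The mixed model keeps women with baseline data only.** True, so a completers-only comparison is not a given. But as described the model does not use attendance. If loss and gain both depend on attendance beyond what baseline explains, the bias remains.
- **Retention work exists.** Calls, home visits and a 95% target are real mitigations. At 95% the illustrated bias is small. Nothing in the documents shows how far a payment would move follow-up from 80% towards 95%, so no such gain is claimed here.
- **Payments to low-income young women, some of them minors, need care.** Average family income is INR 5,900 a month (Section I, item 4, The Study Area). Eight sessions at 200 INR are 1,600/5,900 = 27% of that; one more payment makes it 1,800/5,900 = 31%. This is a fair question for the IRB.

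**Conclusion.** The point holds as a cheap improvement to retention at the post-survey. The documents show that stated payment, tracing and post-survey timing all depend on attendance. They do not show that missing outcomes will track attendance; that is a plausible risk.

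If missing women gain 0-50% of what observed women gain, the overstatement is 3-5% at 95% follow-up and 11-25% at 80%. Both the range for *r* and the idea that losses are mainly low attenders are assumptions.

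A reader might extend the argument to the enrolment survey or the unpaid wait. The documents do not support that. The enrolment survey precedes every session, so loss there cannot depend on attendance, and no survey is scheduled at the end of the wait that an unpaid wait could lose. Nor do the surveys carry all of Aim 2, which also draws on facilitator logs, observations, focus groups and provider surveys.

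Separately, the 2-16 USD range and the 200 INR rate do not agree at the plan's own exchange rates if there are eight sessions.

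**What to change.** 1. Add to Section VI, item 2: *Every enrolled woman receives 200 INR for completing the post-intervention survey, whatever her session attendance.* The protocol already pays this amount for the formative survey.
2. State in the club component of Section I, item 4 and in Section III, item 3a: *The post-intervention survey is offered to all enrolled women at the end of their group's curriculum, including those who stopped attending.* The payment only works with this sentence, since a woman with no survey date cannot earn it. Add survey scheduling to the uses of phone numbers in Section IV, item 1 so that these women can be reached.
3. Reconcile the 2-16 USD range in Section VI, item 3 with the number of sessions, the 200 INR rate and the new payment.

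**Cost:** about 20,000 INR (240-280 USD) if all 100 women complete the survey, and an IRB amendment to the payment schedule. Payment for the enrolment survey or the wait is optional and does not address this bias.
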